9.6. Data management

9.6.1. Case report forms (CRFs)/Data collection tools (DCTs)/Electronic data record

As used in this protocol, the term DCT should be understood to refer to a paper data collection form or an electronic data record or both, depending on the data collection method used in this study.

A completed DCT is required for each included participant. The completed, original DCTs are the sole property of Pfizer and should not be made available in any form to third parties, except for authorized representatives of Pfizer or appropriate regulatory authorities, without written permission from Pfizer. PPD shall ensure that the DCTs are securely stored in encrypted electronic form and will be password protected to prevent access by unauthorized third parties.

PPD has ultimate responsibility for the collection and reporting of all data entered on the DCTs, as required, and ensuring that they are accurate, authentic/original, attributable, complete, consistent, legible, timely (contemporaneous), enduring, and available when required. The DCT serves as the source document. Any corrections to entries made in the DCTs must be dated, initialed, and explained (if necessary) and should not obscure the original entry.

Data for this prospective, observational safety study will be managed with an electronic data capture (EDC) platform that is compliant with 21 Code of Federal Regulations (CFR) Part 11. The variables described in Section 9.4.1 will be solicited and entered in the EDC directly by participants and/or their HCPs or indirectly by VRCC personnel. The data provided by participants and/or their HCPs over the phone or on paper data collection forms, which can be submitted to the VRCC via mail, email or fax, will be reviewed for correctness and completeness and entered into the database by VRCC personnel.

Free-text entries of medical conditions, including AEs and medicinal exposures will be coded using the Medical Dictionary for Regulatory Activities (MedDRA) and World Health Organization (WHO) Drug, respectively. All free-text data will be reported in listings.

9.6.2. Software and hardware

Data analyses will be performed using the statistical software program, SAS (version 9.4 or higher; SAS Institute, Cary, NC).

9.6.3. Record retention

To enable evaluations and/or inspections/audits from regulatory authorities or Pfizer, PPD agrees to keep all study-related records. The records should be retained by PPD according to local regulations or as specified in the vendor contract, whichever is longer. PPD must ensure that the records continue to be stored securely for so long as they are retained.

PFIZER CONFIDENTIAL

If PPD becomes unable for any reason to continue to retain study records for the required period, Pfizer should be prospectively notified. The study records must be transferred to a designee acceptable to Pfizer.

Study records must be kept for a minimum of 15 years after completion or discontinuation of the study, unless PPD and Pfizer have expressly agreed to a different period of retention via a separate written agreement. Records must be retained for longer than 15 years if required by applicable local regulations.

PPD must obtain Pfizer's written permission before disposing of any records, even if retention requirements have been met.

9.7. Data analysis

Detailed methodology for the summary and statistical analyses of the data collected in this study will be documented in a statistical analysis plan (SAP), which will be dated, filed, and maintained by the Sponsor. The SAP may modify the plans outlined in the protocol; any major modifications of primary outcome definitions or their analyses would be reflected in a protocol amendment.

Descriptive analyses for the primary and secondary study objectives will be performed annually for all data; comparative analyses will be conducted for the final analysis.

Registry data will be summarized in tables and listings by study cohort, as appropriate. These data include maternal demographic characteristics and pre-pregnancy anthropometrics, pregnancy information, maternal obstetrical history, family history of congenital malformations, disease information, maternal exposures during pregnancy, pregnancy outcome information, and infant outcome information. For each continuous variable, the number of observations, median, mean, standard deviation, minimum, and maximum will be reported. For each categorical variable, the frequency and percentage in each category will be reported. The frequency and percentage of participants with missing data for each data point will be presented. Results will be rounded to one decimal place; therefore, percentages may not always add up to 100.

Pair-wise comparisons of demographic characteristics, baseline characteristics, and prevalence rates of the outcomes of interest will be conducted between the study cohorts: pregnant women with migraine who were exposed to rimegepant versus pregnant women with migraine who were unexposed to rimegepant.

Comparisons will be conducted using the methods described below, and p-values and 95% CIs will be reported, as appropriate, to reflect statistical uncertainty. The study is not powered for multiple comparisons; thus, p-values associated with secondary outcomes will be nominal. Additional details are provided below and will be provided in the SAP.

PFIZER CONFIDENTIAL

9.7.1. Main analysis population

The main analysis population will include participants who are:

- Valid (Section 9.3.1.1)
- Prospectively enrolled (Section 9.3.1.2)
- Not exposed to other CGRP antagonists, CGRP monoclonal antibodies, and/or ditans after enrollment (Section 9.3.1.3)
- Not considered lost to follow-up (Section 9.3.1.4)

For some outcomes, the main analysis population will be further restricted based on certain relevant factors.

9.7.2. Demographic and baseline characteristics

Demographic and baseline characteristics will be summarized with descriptive statistics, and balance between cohorts will be assessed using standardized differences. These data will be presented before and after balancing using the inverse probability weighting (IPW) method (Section 9.7.3.4). Reasons will be provided for those excluded from the main analysis population (ie, invalid, retrospectively enrolled, lost to follow-up).

9.7.3. Analysis of the outcome measures

9.7.3.1. Comparison with internal comparator cohorts

Formal quantitative comparisons of prevalence rates of the outcomes of interest will be conducted between the study cohorts. The prevalence rates of the outcomes of interest will be calculated as described in Section 9.7.3.3.

For each outcome, if the number of events permits, results will be presented for unadjusted and adjusted models. Summary statistics (relative risk) will be reported along with their 95% CIs and p-values. For the primary outcome, a p-value <0.05 will be considered statistically significant. Exact methods will be used to calculate crude (unadjusted) relative risks for binary outcomes, including MCM, minor congenital malformation, SAB, elective termination, TOPFA, stillbirth, pre-eclampsia, eclampsia, gestational hypertension, gestational diabetes, preterm birth, SGA, postnatal growth deficiency, and infant developmental delay.

Adjusted methods will incorporate weights estimated using the IPW method to balance the cohorts with regard to observable covariates (Section 9.7.3.4). For each binary outcome, a weighted generalized linear model using a binomial family and a log (relative risk) link will be employed to estimate an adjusted relative risk.

PFIZER CONFIDENTIAL

9.7.3.2. Comparison with external comparators

Analyses will also be conducted to compare the prevalence rates of the outcomes of interest among rimegepant-exposed participants of the main analysis population with those of selected external comparators (eg, MACDP, EUROCAT, NVSS), if available. Prevalence rates of the outcomes of interest will be calculated as described in Section 9.7.3.3. These registry prevalence rates will then be compared with those of selected external comparators using Exact methods. Prevalence rates will be reported along with their 95% CIs and p-values for the comparison.

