8.2. Objectives

The purpose of the study is to prospectively evaluate fetal, maternal, and infant outcomes through 12 months of age in women with migraine who were exposed to rimegepant during pregnancy or just prior to pregnancy (up to 3 days prior to conception) (hereinafter referred to in the main text as "pregnant women with migraine who were exposed to rimegepant"), as well as in 2 comparison groups of women with and without migraine who were not exposed to rimegepant during pregnancy.

The primary objective is to compare the occurrence of MCMs in the fetuses/infants of women with migraine who were exposed to rimegepant during pregnancy or just prior to pregnancy (up to 3 days prior to conception) to: 1) an internal comparator cohort of women with migraine who were not exposed to rimegepant during pregnancy or just prior to pregnancy (up to 5 product half-lives prior to conception) (hereinafter referred to in the main text as "pregnant women with migraine who were unexposed to rimegepant") and 2) an external comparator cohort of pregnant women without migraine.

The secondary objectives are to compare the occurrence of the secondary outcomes in women with migraine who were exposed to rimegepant during pregnancy or just prior to pregnancy (up to 3 days prior to conception) to: 1) an internal comparator cohort of women with migraine not exposed to rimegepant during pregnancy or just prior to pregnancy (up to 5 product half-lives prior to conception) and 2) an external comparator cohort of pregnant women without migraine.

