9.2.3.2. External comparator group

For the external comparator group (pregnant women without migraine), the retrospective pregnancy outcomes study (NDA 212728, post-marketing requirement 3799-7, Pfizer study C4951006 [formerly BHV3000-403]) will serve as a resource for outcome rates of MCM, SAB, elective termination, stillbirth, pre-eclampsia/eclampsia, preterm birth, and SGA. Women in this cohort may or may not be exposed to medications. The retrospective pregnancy outcomes study will be conducted in parallel to the registry and is specifically designed to complement the registry by monitoring these outcomes in a comparison group without migraine, providing annual updates in the interim reports until the study is completed. Additionally, appropriate published studies reporting representative rates will be selected to serve as comparators.

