9.9. Limitations of the research methods

As participation in the study will be voluntary, the included participants may not be representative of the overall population of pregnant women in the US and EU. Because early prenatal testing is so prevalent, it would be difficult to achieve adequate numbers of prospectively enrolled pregnant women if all pregnancies with prior prenatal testing were excluded from the analysis. Therefore, the primary analysis will include all pregnancies enrolled, regardless of prenatal testing. Pregnancies enrolled after prenatal testing but prior to outcome, as well as those who enroll after prenatal diagnosis of any major malformation, will be evaluated in sensitivity analyses. As reporting of pregnancies is totally voluntary, it is possible that even in prospectively reported cases, potential bias could exist. For example, high-risk pregnancies (ie, one that threatens the health or life of the mother or her fetus) or low-risk pregnancies may be more likely to enroll. Baseline characteristics will be evaluated to identify whether such selection bias may be present.

Those pregnancies that have reached EDD, but for which pregnancy outcome information was unobtainable, will be considered lost to follow-up. It is possible that outcomes among pregnancies lost to follow-up could differ from those with documented outcomes. Due to differences in individual reporting patterns, it is currently not possible to assess with any certainty what impact the potential biases the losses to follow-up may have on the analysis. However, the proportion of pregnancies lost to follow-up in each cohort will be compared to examine differential loss to follow-up, and the characteristics of those lost to follow-up will be compared to those not lost to follow-up within each cohort to address this potential source of bias.

The percentage of fetal losses (SABs, elective terminations, stillbirths, etc.) with MCMs is unknown. The data collection form attempts to obtain information on MCMs detected at the time of the outcome; however, the reporting physician may not know the condition of the aborted fetus.

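### The external half of the primary objective is analysed only as a crude comparison of prevalence with p-values, so case-mix differences can appear as, or mask, a drug effect

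*Protocol*

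**What the plan says.** Section 8.2 sets two comparators for major congenital malformations (MCM): the internal unexposed migraine cohort and "2) an external comparator cohort of pregnant women without migraine". The secondary objectives use the same pair.

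For the external comparison, Section 9.7.3.2 says: "These registry prevalence rates will then be compared with those of selected external comparators using Exact methods". It adds: "Prevalence rates will be reported along with their 95% CIs and p-values for the comparison". No covariate is named.

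Adjustment appears in Section 9.7.3.1, on the internal comparison: "Adjusted methods will incorporate weights estimated using the IPW method to balance the cohorts with regard to observable covariates". Section 9.7 spells out which cohorts are meant: "pregnant women with migraine who were exposed to rimegepant versus pregnant women with migraine who were unexposed to rimegepant".

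Section 9.7.3.3 and Table 4 match the numerator and denominator conventions to each external source, including study C4951006. Of that study, Section 9.2.3.2 says: "The retrospective pregnancy outcomes study will be conducted in parallel to the registry and is specifically designed to complement the registry".

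Section 9.9 accepts that "the included participants may not be representative of the overall population of pregnant women", and Section 9.2.3.3 concedes demographic and geographic limits of MACDP.

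**The concern.** The protocol considers imbalance likely enough between two cohorts that share a disease and a registry to require weighting (Section 9.7.3.4). The external populations share neither, yet that comparison gets no adjustment and still produces a p-value.

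Three differences are foreseeable from the text:

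- **Maternal age.** The MACDP and EUROCAT comparisons count chromosomal malformations (Section 9.3.4.1 and Table 4), so age matters most there.
- **Calendar year.** The registry enrols from September 2021 and collects data until April 2034. One source cited for the 3% MCM rate covers 1978-2005. Whether the same source will be the comparator is not stated.
- **Plurality.** Section 9.3.1.5 limits the preterm birth and small-for-gestational-age analyses to singletons because multiples carry higher risk. The C4951006 rows of Table 4 for these outcomes drop that limit.

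At stake is half of the primary objective. An excess may be reported that the drug did not cause, or a real excess may be diluted.

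**Working it through.** **1. The plan's own figures.** Section 9.5.2 gives power for the internal comparison only. Two-sided normal approximation with pooled variance, alpha 0.05:

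- 390 per cohort, 3% vs 7.5%: 80.56% (Table 2: 80.6%).
- 316 per cohort, 3% vs 8.1%: 80.10% (Table 2: 80%).
- Evaluable number: 390 × 0.9 × 0.9 = 315.9, so 316.

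These reproduce. No operating characteristic is given for the external comparison.

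**2. Illustrative external test for MCM.** Inputs: n = 316 and an external rate of 3% (both Section 9.5.2), with that rate treated as fixed and known. The test is an exact two-sided binomial test at 0.05. Expected cases are 316 × 0.03 = 9.48. The test is significant on the high side from 16 cases, an observed ratio of (16/316)/0.03 = 1.69.

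**3. Chance of a significant excess with no drug effect.** This is P(X ≥ 16) for X ~ Binomial(316, 0.03 × c), where c is the case-mix ratio (expected registry risk over external risk). The documents give no value for c, so these are assumptions:

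| c | P(significant excess) |
|---|---|
| 1.0 | 3.1% |
| 1.1 | 6.2% |
| 1.2 | 11.0% |
| 1.3 | 17.6% |

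**4. Age alone.** Let a be the external share aged 35 or over, b the registry share, and R the relative risk of MCM at that age. Then c = (1 + b(R − 1)) / (1 + a(R − 1)). Assume a = 0.20, b = 0.30-0.40 and R = 1.2-2.0:

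- Low end: 1.06/1.04 = 1.02, giving 3.6%.
- High end: 1.40/1.20 = 1.17, giving about 9%.

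Age by itself therefore moves the false-excess rate from about 3% to about 4-9%.

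**5. Opposite direction.** With a true doubling of risk and no case-mix difference (rate 0.06), P(X ≥ 16) is 79%. If case mix lowers expected risk by an assumed 20% (rate 0.048), it falls to 45%.

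Table 4 limits the MACDP and EUROCAT rows to first-trimester exposure, so the real n there may be below 316.

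**The case against.** **Deferral to the SAP.** Section 9.7 leaves detailed methods to the SAP, and an observed/expected ratio with an exact interval is itself an exact method. So the protocol does not forbid standardization, and a reader should not infer that it does. But it sets out crude and weighted analyses for one comparison and only exact methods for the other, and Section 9.7.3.1 uses exact methods for crude estimates. That is a stated choice, not mere silence.

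**Context rather than inference.** Section 9.9 uses external data partly to contextualize results, Section 9.2.5 reviews representativeness in each interim report, secondary p-values are nominal, and the 0.05 significance rule appears only in the internal section. This lowers the stakes. It does not alter Section 8.2, which makes the external comparison part of the primary objective, or the p-values promised for it.

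**Larger readings that the documents do not support.** A reader might extend the illustration to preterm birth at 8.47% and obtain much higher false-excess rates. The only external preterm row in Table 4 is C4951006, a study with its own sampling error and no stated size or rate, so a test against a fixed 8.47% is not the planned test. Gestational diabetes is not among the outcomes C4951006 supplies; its Table 4 comparator is NVSS, on live births. A reader might also infer that case mix will create a false signal. The direction is unknown, and age alone probably shifts overall MCM only modestly.

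**A partial remedy.** Section 7.3 reports migraine associated with hypertensive disorders, miscarriage and preterm birth, though not with MCM, in a cohort matched on age and conception year. Standardization leaves that difference in place. This stands.

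**Conclusion.** The concern holds in a limited form. The external half of the primary objective is specified as a crude comparison with p-values, and nothing stated accounts for maternal age, calendar year or plurality. For MCM the false-excess chance goes from about 3% to 6-18% under an assumed 10-30% case-mix shift, and to about 4-9% for age alone under assumed age shares and age effects. All case-mix inputs are assumptions, the external rate is treated as fixed, and bias could run either way. The weighted internal comparison is unaffected, so this is a worthwhile correction and not a flaw that undermines the study.

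**What to change.** 1. For the outcomes C4951006 supplies (MCM, spontaneous abortion, elective termination, stillbirth, pre-eclampsia/eclampsia, preterm birth, small for gestational age), add a comparison standardized or stratified by the maternal-age bands of Section 9.7.3.5, calendar year, and singleton versus multiple, where that study's data allow. Report observed/expected with a confidence interval beside the crude result, allowing for C4951006's own sampling error.
2. Do the same for published sources that give age-specific rates, with MACDP and EUROCAT first.
3. Label the remaining external comparisons as unadjusted and descriptive.
4. State that standardization does not remove the effect of migraine itself.

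The registry already collects maternal age, calendar year at conception and number of fetuses (Section 9.3.5). The cost is a stratified tabulation from C4951006 and revised analysis wording. That the tabulation can be obtained is an assumption, resting on C4951006 being the sponsor's own parallel study; its available strata are not described. The downside is sparse strata and slightly wider intervals.

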9.7.3.3. Calculation of outcome prevalence

Prevalence rates of the outcomes of interest will be calculated according to the conventions described in Table 4. In general, the prevalence of each outcome will be calculated by dividing the number of cases of the outcome by the appropriate denominator for that particular outcome, based on clinical knowledge and/or the methodology used by the external comparator. Prevalence is preferred over incidence when examining pregnancy outcomes, such as congenital malformations, because incidence cannot be reliably estimated given the complexities in the reproductive process.⁶⁷

For most outcomes, the main analysis population (denominator) will be the number of pregnant women with pregnancy outcome data, the number of live births, or the number of infants with follow-up data at the timepoint of interest, as appropriate; however, for some outcomes, the main analysis population (denominator) will be restricted based on certain relevant factors:

- For MCM, prevalence in the rimegepant-exposed cohort will be calculated among the subset of women who are exposed during the first trimester.
- For MCM, prevalence will be calculated among live births for the primary analysis, and a secondary analysis will be conducted among live births and fetal losses.
- For preterm birth, SGA, and postnatal growth deficiency, prevalence will be calculated among singleton live births due to the higher risk of these outcomes in twins and higher-order multiples.
- For live birth and infant outcomes (ie, preterm birth, SGA, postnatal growth deficiency, and infant developmental delay), prevalence will be calculated among live births/infants without MCMs.
- For postnatal growth deficiency, infants born preterm or SGA will be excluded from the main analysis population (denominator).
- For infant developmental delay, infants born preterm will be excluded from the main analysis population (denominator).
- For SAB and preterm birth, prevalence will be calculated among the subset of women who are enrolled in the registry prior to 20 and 37 gestational weeks, respectively.
- For some outcomes, prevalence will be calculated at multiple timepoints. For example, postnatal growth deficiency and infant developmental delay will be assessed at 2, 4, 6, and 12 months of

PFIZER CONFIDENTIAL

infant age. At each timepoint, prevalence will be calculated among infants with data available for the particular outcome at that timepoint.

For comparison with external comparators, the prevalence rates of the outcomes of interest among the rimegepant-exposed participants of the main analysis population will be calculated according to the conventions used by the selected external comparators. For example, for the comparison with MACDP, live births and stillbirths with MCMs (including MCMs not associated with medication exposure) will be included in the numerator, and the denominator will be the number of live births. The MACDP calculates rates by this convention, which increases sensitivity. Likewise, for comparisons with the external cohort of pregnant women without migraine (from the retrospective pregnancy outcomes study), the conventions used to calculate outcome prevalence rates in the internal and external cohort will be aligned.

In addition, "crude" prevalence rates, without limitations and exclusions, may be conducted to avoid restricting the main analysis population (denominator). For example, infants with MCM and/or infants born preterm may be included for the prevalence rate calculation of infant developmental delay.

Outcome	Numerator	Denominator	
Primary Outcome – MCM			
Primary analysis: among live births with 1 st trimester exposure (if applicable for cohort)	Live births with confirmed MCMs (excluding MCMs not associated with medication exposure) among women with pregnancy outcome data and exposure during 1 st trimester (if applicable)	Live births among women with pregnancy outcome data and, if applicable, exposure during 1 st trimester	
Secondary analysis: among all pregnancy outcomes with 1 st trimester exposure (if applicable for cohort)	Live births and fetal losses with confirmed MCMs (excluding MCMs not associated with medication exposure) among women with pregnancy outcome data and, if applicable, exposure during 1 st trimester	Live births and fetal losses among women with pregnancy outcome data and, if applicable, exposure during 1 st trimester	
Secondary analysis: among live births with exposure at any time during pregnancy (if applicable for cohort)	Live births with confirmed MCMs (excluding MCMs not associated with medication exposure) among women with pregnancy outcome data and, if applicable, exposure at any time during pregnancy	Live births among women with pregnancy outcome data and, if applicable, exposure at any time during pregnancy	
Secondary analysis: among all pregnancy outcomes with exposure at any time during pregnancy (if applicable for cohort)	Live births and fetal losses with confirmed MCMs (excluding MCMs not associated with medication exposure) among women with pregnancy outcome data and, if applicable, exposure at any time during pregnancy	Live births and fetal losses among women with pregnancy outcome data and, if applicable, exposure at any time during pregnancy	

Table 4.	Calculation of Outcome Prevalence
----------	------------------------------------------

PFIZER CONFIDENTIAL

Outcome	Numerator	Denominator
Comparison with external comparator (CDC MACDP)	Live births and stillbirths with confirmed MCMs (including MCMs not associated with medication exposure) among women with pregnancy outcome data and exposure during the 1 st trimester	Live births among women with pregnancy outcome data and exposure during the 1 st trimester
Comparison with external comparator (Pfizer Study C4951006 [formerly BHVN Outcomes Study])	Live births with confirmed MCMs (excluding MCMs not associated with medication exposure) among women with pregnancy outcome data and exposure at any time during pregnancy	Live births among women with pregnancy outcome data and exposure at any time during pregnancy
Comparison with EUROCAT	Live births and stillbirths and TOPFA with confirmed MCMs (including MCMs not associated with medication exposure) among women with pregnancy outcome data and exposure during the 1 st trimester	Live births and stillbirths among women with pregnancy outcome data and exposure during the 1 st trimester
Secondary Outcomes		
Minor congenital malformations	Live births with minor congenital malformations among women with pregnancy outcome data	Live births among women with pregnancy outcome data
Gestational diabetes		
Primary analysis between internal cohorts	Gestational diabetes among women with pregnancy outcome data	Women with pregnancy outcome data
Comparison with external comparator (CDC NVSS)	Gestational diabetes among live births	Live births among women with pregnancy outcome data
Gestational hypertension		
Primary analysis between internal cohorts	Gestational hypertension among women with pregnancy outcome data	Women with pregnancy outcome data
Comparison with external comparator ⁶¹	Gestational hypertension among live births	Live births among women with pregnancy outcome data
Pre-eclampsia		
Primary analysis between internal cohorts	Pre-eclampsia among women with pregnancy outcome data	Women with pregnancy outcome data
Eclampsia	·	
Primary analysis between internal cohorts	Eclampsia among women with pregnancy outcome data	Women with pregnancy outcome data
Comparison with external comparator ⁶¹	Eclampsia among live births	Live births among women with pregnancy outcome data
Pre-eclampsia/eclampsia	•	
Primary analysis between internal	Pre-eclampsia or eclampsia among	Women with pregnancy outcome

PFIZER CONFIDENTIAL

Outcome	Numerator	Denominator
cohorts	women with pregnancy outcome data	data
Comparison with external comparator (Pfizer Study C4951006)	Pre-eclampsia or eclampsia among women with pregnancy outcome data	Women with pregnancy outcome data
SAB		
Primary analysis between internal cohorts	SABs among women with pregnancy outcome data who are enrolled (and exposed, if applicable) prior to 20 gestational weeks	Women with pregnancy outcome data who are enrolled (and exposed, if applicable) prior to 20 gestational weeks
Comparison with external comparator (Pfizer Study C4951006)	SABs among women with pregnancy outcome data who are enrolled (and exposed, if applicable) prior to 20 gestational weeks	Women with pregnancy outcome data who are enrolled (and exposed, if applicable) prior to 20 gestational weeks
Stillbirth		
Primary analysis between internal cohorts	Stillbirths among women with pregnancy outcome data	Women with pregnancy outcome data
Comparison with external comparator (CDC NVSS)	Stillbirths among women with pregnancy outcome data	Live births and stillbirths among women with pregnancy outcome data
Comparison with external comparator (Pfizer Study C4951006)	Stillbirths among women with pregnancy outcome data	Women with pregnancy outcome data
Elective termination		
Primary analysis between internal cohorts	Elective terminations among women with pregnancy outcome data	Women with pregnancy outcome data
Comparison with external comparator (CDC Abortion Surveillance System)	Elective terminations among women with pregnancy outcome data	Live births among women with pregnancy outcome data
Comparison with external comparator (Pfizer Study C4951006)	Elective terminations among women with pregnancy outcome data	Women with pregnancy outcome data
TOPFA		
Primary analysis between internal cohorts	TOPFA among women with pregnancy outcome data	Women with pregnancy outcome data
Comparison with external comparator (EUROCAT) ⁴⁴	TOPFA among women with pregnancy outcome data	Live births and stillbirths among women with pregnancy outcome data
Preterm birth		
Primary analysis between internal cohorts	Singleton preterm live births without MCMs among women with pregnancy outcome data who are enrolled (and exposed, if applicable) prior to 37 gestational weeks	Singleton live births without MCMs among women with pregnancy outcome data who are enrolled (and exposed, if applicable) prior to 37 gestational weeks
Comparison with external comparator (Pfizer Study C4951006)	Preterm live births among women with pregnancy outcome data who are	Live births among women with pregnancy outcome data who are

PFIZER CONFIDENTIAL

Outcome	Numerator	Denominator
	enrolled (and exposed, if applicable) prior to 37 gestational weeks	enrolled (and exposed, if applicable) prior to 37 gestational weeks
SGA		
Primary analysis between internal cohorts	Singleton live births without MCMs who are SGA based on weight/length/head circumference among women with pregnancy outcome data	Singleton live births without MCMs with weight/length/head circumference data among women with pregnancy outcome data
Comparison with external comparator (Pfizer Study C4951006)	Live births who are SGA based on weight among women with pregnancy outcome data	Live births among women with pregnancy outcome data
Postnatal growth deficiency		
Primary analysis between internal cohorts (at 2, 4, 6, and 12 months)	Singleton infants without MCMs who were not born preterm or SGA with postnatal growth deficiency based on weight/length/head circumference among infants with weight/length/head circumference data at the time point	Singleton infants without MCMs who were not born preterm or SGA with weight/length/head circumference data at the time point
Infant developmental delay	-	
Primary analysis between internal cohorts (at 2, 4, 6, and 12 months)	Infants without MCMs who were not born preterm with developmental delay in a particular category among infants with developmental milestone data for the category at the time point	Infants without MCMs who were not born preterm with developmental milestone data for the category at the time point

CDC = US Centers for Disease Control and Prevention; EUROCAT = European Surveillance of Congenital Anomalies; MACDP = Metropolitan Atlanta Congenital Defects Program; MCM = major congenital malformation; NVSS = National Vital Statistics System; SAB = spontaneous abortion; SGA = small for gestational age; TOPFA = termination of pregnancy for fetal anomaly

